## 7 STUDY PROCEDURES

### 7.1 STUDY DIAGRAM

Patient Flow Diagram

### 7.2 STEP 1

Written informed consent will be obtained prior to the conduct of any study procedure. Potential study participants will undergo eligibility screening (see Section 5.2.1.) by an interviewer. Eligibility will be determined based on participant responses to an interviewer-administered eligibility checklist. Study Step 1 activities will be conducted at the following sites: EPICENTRO, VIA LIBRE and IMPACTA San Miguel Clinical Research Site and IMPACTA Barranco Clinical Research Site.

#### 7.2.1 Clinical Procedures

The following procedures will be performed at Step 1 Visit:

1. Explain the purpose of the visit and the informed consent and eligibility determination processes;
2. Determine eligibility, using Screening Eligibility Checklist (interviewer-administered);
3. Ascertain participant identity and assign Participant ID (PID) number;

4. Obtain written informed consent for willingness to consider study participation;
5. Deliver HIV and STD pre-test and risk reduction counseling; obtain written informed consents for HIV testing and stored blood for future testing. HIV and STD counseling includes encouraging, training in, and negotiation of condom use with partners and provision of lubricated condoms. Counselors will also discuss risk reduction by discussion of HIV serostatus and risks with new and existing partners, reduction of number of sexual partners, and the importance of prompt treatment for STDs;
6. Collect participant contact and locator information;
7. Administer Screening Questionnaires
8. Obtain 18.5 ml of venous blood for HIV and syphilis testing; and if acute or recent HIV infection is detected, other blood tests to evaluate overall health. These tests include liver function, Hepatitis B serology and HIV RNA;
9. Administer complete physical exam;
10. Provide results on HIV rapid test (per study HIV diagnosis algorithm –Section 7.1.) and syphilis test (diagnosis following Ministry of Health of Peru guidelines); and deliver post-test counseling;
11. Deliver counseling on potential strategies for re-contacting HIV seronegative individuals with evidence of acute infection (HIV-1 RNA positive) for further HIV testing and linkage to care;
12. Provide study site contact information and instruct the participant to contact the study site for additional information or counseling, if needed;
13. Refer for STD treatment or treat according to Ministry of Health of Peru guidelines
14. If no HIV infection is diagnosed and eligibility criteria are met (see Section 5.2.), refer to Step 2 and schedule a First Visit to occur in 30 days (+/- 15 days);
15. If acute or recent HIV infection is diagnosed, refer to Step 3: Participants will be asked to come to the IMPACTA Barranco or IMPACTA San Miguel Clinical Research Site as described in the Study Specific Procedures;
16. If chronic HIV infection is diagnosed, participant is not eligible for study participation. Participant should be referred to other sources of HIV care, including standard care at no charge under Peruvian guidelines or to other studies if available;
17. Document all referrals;
18. Complete and enter all required data collection forms.

## **7.2.2 Laboratory Evaluations**

### **1. HIV testing**

The following tests will be used for establishing HIV status in this protocol: Determine™ HIV-1/2 [Alere/Abbott Laboratories] (third-generation HIV test), GS HIV Combo Ag/Ab EIA [Bio-Rad] (fourth-generation HIV test) and Liat™ HIV Quant Assay [IQuum] (HIV-1 RNA test) will be used in this algorithm (see Section 7.1).

### **2. Sexually Transmitted Infection Testing**

Syphilis screening testing will be conducted by RPR and confirmed by MHA-TP if reactive. Syphilis diagnosis and treatment will follow Ministry of Health of Peru guidelines.

## **7.3 STEP 2**

### **7.3.1 Regular Follow-Up Visit**

Participants who test HIV-uninfected in Step 1 and still meet eligibility criteria (see Section 5.2.2.) will be followed in a prospective cohort study. Study Step 2 activities will be conducted at the following sites: EPICENTRO, VIA LIBRE, IMPACTA San Miguel Clinical Research Site and IMPACTA Barranco Clinical Research Site. The follow-up of participants will be every 30 days. At each follow-up visit, the following procedures will be performed:

1. Confirm participant identity and PID number;
2. Update locator information;
3. Administer Follow-up Questionnaire for assessment of sexual risk behavior and socialization venues;
4. Deliver HIV and STD pre-test and risk reduction counseling; obtain written informed consents for HIV testing.. HIV and STD counseling includes encouraging, training in, and negotiation of condom use with partners and provision of lubricated condoms. Counselors will also discuss risk reduction by discussion of HIV serostatus and risks with new and existing partners, reduction of number of sexual partners, and the importance of prompt treatment for STDs;
5. Obtain 18.5 ml of venous blood for HIV and syphilis testing (every 3 months) and if acute or recent HIV infection is detected, other blood tests to evaluate overall health. These tests include liver function, Hepatitis B serology and HIV RNA;
6. Administer targeted physical exam, if symptoms are reported;
7. Provide results on HIV rapid test (per study HIV diagnosis algorithm – Section 7.1), and syphilis test (diagnosis following Ministry of Health of Peru guidelines); and deliver post-test counseling;
8. Deliver counseling on potential strategies for re-contacting HIV seronegative individuals with evidence of acute infection (HIV-1 RNA positive) for further HIV testing and linkage

to care;

9. Provide study site contact information and instruct the participant to contact the study site for additional information or counseling, if needed;
10. Refer for STD treatment or treat according to Ministry of Health of Peru guidelines;
11. If no HIV infection diagnosis schedule a Step 2 Follow-up Visit to occur in 30 days (+/- 15 days).
12. If acute or recent HIV infection diagnosed, participants will be asked to come to the IMPACTA Barranco or IMPACTA San Miguel Clinical Research Site as described in the Study Specific Procedures;
13. If chronic HIV infection is diagnosed, participant is not eligible for inclusion in the study. Participant should be referred to other sources of HIV care, including regular care or other studies if available;
14. Document all referrals;
15. Confirm schedule for next quarterly visit;
16. Complete and enter all required data collection forms.

### **7.3.2 Interim Contacts and Visits**

Interim contacts and visits may be conducted at participant request at any time during Step 2. Interim HIV/STD counseling and testing should be provided as needed in response to participant reports a potential high risk sexual exposure, STD symptoms, partner of a newly-diagnosed person with acute or recent HIV infection; symptoms of acute retroviral syndrome. All interim contacts and visits will be documented in participants' study records.

### **7.3.3 Laboratory Evaluations**

Laboratory evaluation will follow what is described in Section 7.2.2.

## 7.4 STEP 3

### 7.4.1 Timing of Visits

Those participants, who have initiated their participation in the study before the approval of Amendment Letter #1 in this study protocol, will continue their participation as originally programmed and is described here below.

Procedure	Study Visit															
	Week															
	0	1	2	4	6	8	12	16	20	24	28	32	36	40	44	48
Enrolment and sample storage informed consents		X														
Acute or recent HIV-1 counseling		X	X	X	X	X	X	X	X	X	X	X	X	X	X	X
Clinical assessment		X	X	X	X	X	X	X	X	X	X	X	X	X	X	X
TB screening		X***														
CBC		X			X		X	X			X					X
Chemistry/LFT				X		X	X			X						X
Lipid panel		X***					X			X						X
Urinalysis		X		X		X				X						X
Hepatitis B serology																
STI testing		X					X			X						X
CD4+/CD8+ cells count		X			X		X			X			X			X
Plasma HIV-1 RNA		X	X	X	X	X	X	X	X	X	X		X			X
Semen and rectal secretion collection		X	X	X	X	X	X	X	X	X	X		X			X
Screening questionnaire - Demographics		X														
AUDIT		X														
Interviewer – Monthly questionnaire*		X			X		X	X	X	X	X	X	X	X	X	X
Quarterly questionnaire**		X					X			X			X			X
Pharmacy Refills				X		X	X	X	X	X	X	X	X	X	X	X
Blood volumes (ml)	60.0	10	10	21.5	10	21.5	21.5	10	10	21.5	0	0	13	0	0	21.5

\*Monthly interviewer-administered questionnaire containing: Timeline Follow Back (alcohol use and sexual behavior), Visual analog scale for ART adherence, and Medication adherence program choices

\*\*Quarterly questionnaire containing: Drug and alcohol use (drug use history, DAST 10, drinking expectancies); Mental health and wellbeing (RAND 12, Social support scale, Stigma scale, Stigma and disclosure, Partner notification, Intimate partner violence, 10 item CES-D, CID Mental health items on anxiety, stress & coping; Medical care (Hospitalization and ER use, Barriers to care, Access to care, Self-efficacy for ART use). \*\*\* These will be done within 72 hours.

*Test and Treat Early HIV among MSM and Transgender Women in Lima, Peru*

Once the Amendment Letter #1 for this study has been approved, the participants who are eligible will enter Step 3 and they will be participate in the following way:

Procedure	Week																	
	0	1	2	4	6	8	12	16	20	24	25	26	28	32	36	40	44	48
Enrolment and sample storage informed consents	X																	
Acute or recent HIV-1 counseling	X	X	X	X	X	X	X	X	X	X			X	X	X	X	X	
Clinical assessment	X	X	X	X	X	X	X	X	X	X			X	X	X	X	X	
TB screening	X***																	
CBC	X			X		X	X			X							X	
Chemistry/LFT				X		X	X			X							X	
Lipid panel	X***						X			X							X	
Urinalysis	X			X			X			X							X	
Hepatitis B serology																		
STI testing	X						X			X							X	
CD4+/CD8+ cells count	X			X			X			X					X		X	
Plasma HIV-1 RNA	X	X	X	X	X	X	X	X	X	X					X		X	
Semen and rectal secretion collection	X	X	X	X	X	X	X	X	X	X					X		X	
Screening questionnaire - Demographics	X																	
AUDIT	X																	
Interviewer – Monthly questionnaire*	X			X		X	X	X	X				X	X	X	X	X	
Quarterly questionnaire**	X					X			X					X			X	
Pharmacy Refills				X		X	X	X	X				X	X	X	X	X	
Hair Sample	X					X			X					X			X	
Blood volumes (ml) for participants with immediate treatment	160	60	60	71.5	10	121.5	21.5	110	10	121.5	50	50	50	100	13	100	0	121.5
Blood volumes (ml) for participants with deferred treatment	230	60	60	71.5	0	201.5	21.5	190	10	201.5	50	50	50	100	13	100	0	121.5

\*Monthly interviewer-administered questionnaire containing: Timeline Follow Back (alcohol use and sexual behavior), Visual analog scale for ART adherence, and Medication adherence program choices

\*\*Quarterly questionnaire containing: Drug and alcohol use (drug use history, DAST 10, drinking expectancies); Mental health and wellbeing (RAND 12, Social support scale, Stigma scale, Stigma and disclosure, Partner notification, Intimate partner violence, 10 item CES-D, CID Mental health items on anxiety, stress & coping; Medical care (Hospitalization and ER use, Barriers to care, Access to care, Self-efficacy for ART use). \*\*\* These will be done within 72 hours.

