##### **6.3.1.3 Duration**

Those participants, who have started their participation in the study before the approval of **Amendment Letter #1** in this study protocol, will continue their participation as originally programmed.

Once the Amendment Letter #1 is approved for this study protocol, the participants who have been diagnosed with **acute HIV infection**, and decide to participate in the study will receive treatment duration of 48 weeks.

For the people who are diagnosed with **recent HIV infection** and decide to participate, treatment will depend on which arm they are assigned to:

Arm 1 will receive study treatment for 48 weeks. Arm 2 will receive no treatment for 24 weeks and then receive 24 weeks of study treatment. However, if during the first 24 weeks of no treatment, clinical, virologic, or immunologic criteria of treatment initiation are met, subject will be offered treatment initiation. ART will be provided by the study for the duration of the time that the participant remains in the study. At the end of study, participants will continue ART from other sources.

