## **7.4.2 Timing of Evaluations**

### **7.4.2.1 Entry Evaluations (Week 0 Visit)**

Subjects diagnosed with acute HIV infection must begin treatment within 72 hours after randomization, and preferably within 24 hours. Subjects randomized to Arm 1 must begin treatment within 72 hours after randomization, and preferably within 24 hours.

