### **7.4.2.2 On-Study Evaluations**

On-study evaluations will occur according to the schedule of events as specified in Section 7.4.1. On-study evaluations will occur according to the schedule of events as specified in Section 7.4.1. according to whether the participant was enrolled before or after the approval of Amendment 1, of this protocol. A study visit will be considered missed if it is not completed before half of the time between the current and next study visit has elapsed.

. Study visit windows will be +/- 5 days for scheduled study visits.

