**7.4.3.6 *Laboratory Evaluations***

The "Division of AIDS Table for Grading the Severity of Adult and Pediatric Adverse Events Version 1.0, December, 2004; Clarification August 2009" must be used and is available at <http://rsc.tech-res.com/safetyandpharmacovigilance>.

All laboratory values must be documented in the subject's record and recorded on the CRFs. Subsequently, all laboratory values must be documented in the subject's record, but unless otherwise specified, only laboratory values Grade  $\geq 3$  must be recorded on the CRFs. Any laboratory toxicity that led to a change in treatment, regardless of grade, must be recorded on the CRFs. Laboratory evaluations that do not have a grading scale in the "Division of AIDS Table for Grading the Severity of Adult and Pediatric Adverse Events Version 1.0, December, 2004; Clarification August 2009" must be collected on the CRFs if the values are outside the upper or lower limit of normal. All values for total HDL and LDL cholesterol, and triglycerides should be recorded on the CRFs at baseline and every 12 weeks, regardless of toxicity grade.

1. Hematology

Hemoglobin, white blood cell count, absolute neutrophil count, platelets;

2. Blood chemistries

Serum amylase, lipase, bicarbonate, phosphorus, creatinine, AST (SGOT), ALT (SGPT), alkaline phosphatase.

3. Lipid panel

Subjects should be fasting for at least 8 hours when possible. Triglycerides, total cholesterol, HDL, LDL;

4. Urinalysis

Dipstick, and microscopic exam if dipstick positive;

5. Hepatitis B serology

Potential participants will be tested for hepatitis B infection through HBsAg, anti-HBc and anti-HBs. The interpretation of the results will be based in the US Center for Diseases Control and Prevention Hepatitis B Serology Interpretation (available at <http://www.U.S.Center for Disease Control and Prevention.gov/hepatitis/HBV/HBVfaq.htm#general>).

Individuals with chronic or acute hepatitis B infection will not be eligible to participate. Hepatitis B susceptible participants will be offered hepatitis B vaccination according Ministry of Health of Peruvian guidelines.

6. Sexually transmitted infection testing

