#### **8.5 NEW ONSET OR WORSENING RENAL IMPAIRMENT**

Renal impairment, including cases of acute renal failure and Fanconi syndrome (renal tubular injury with severe hypophosphatemia), has been reported with the use of tenofovir DF, and it's formulations. Estimated creatinine clearance, urine glucose and urine protein should be documented in all patients prior to initiating therapy. Initiation of co-formulated elvitegravir/cobicistat/emtricitabine/tenofovir disoproxil fumarate in patients with estimated creatinine clearance below 70 mL per minute is not recommended.

Co-formulated elvitegravir/cobicistat/emtricitabine/tenofovir disoproxil fumarate and co-formulated emtricitabine/tenofovir DF/efavirenz should be avoided with concurrent or recent use of a nephrotoxic agent (e.g., high-dose or multiple non-steroidal anti-inflammatory drugs (NSAIDs)). Cases of acute renal failure after initiation of high dose or multiple NSAIDs have been reported in HIV-infected patients with risk factors for renal dysfunction who appeared

stable on tenofovir DF. Some patients required hospitalization and renal replacement therapy. Alternatives to NSAIDs should be considered, if needed, in patients at risk for renal dysfunction. Persistent or worsening bone pain, pain in extremities, fractures and/or muscular pain or weakness may be manifestations of proximal renal tubulopathy and should prompt an evaluation of renal function in at-risk patients.

Routine monitoring of estimated creatinine clearance, urine glucose, and urine protein should be performed during co-formulated elvitegravir/cobicistat/emtricitabine/tenofovir disoproxil fumarate therapy in all patients. Additionally, serum phosphorus should be measured in patients at risk for renal impairment.

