## **8.6 SKIN RASH**

In controlled clinical trials, 26% (266/1008) of patients treated with 600 mg efavirenz experienced new-onset skin rash compared with 17% (111/635) of patients treated in control groups. Rash associated with blistering, moist desquamation, or ulceration occurred in 0.9% (9/1008) of patients treated with efavirenz. The incidence of Grade 4 rash (e.g., erythema multiforme, Stevens-Johnson syndrome) in patients treated with efavirenz in all studies and expanded access was 0.1%. Rashes are usually mild-to-moderate maculopapular skin eruptions that occur within the first 2 weeks of initiating therapy with efavirenz (median time to onset of rash in adults was 11 days) and, in most patients continuing therapy with efavirenz, rash resolves within 1 month (median duration, 16 days). The discontinuation rate for rash in clinical trials was 1.7% (17/1008). Co-formulated emtricitabine/tenofovir DF/efavirenz can be reinitiated in patients interrupting therapy because of rash.

Co-formulated emtricitabine/tenofovir DF/efavirenz should be discontinued in patients developing severe rash associated with blistering, desquamation, mucosal involvement, or fever. Appropriate antihistamines and/or corticosteroids may improve the tolerability and hasten the resolution of rash.

Experience with efavirenz in patients who discontinued other antiretroviral agents of the NNRTI class is limited. Nineteen patients who discontinued nevirapine because of rash have been treated with efavirenz. Nine of these patients developed mild-to-moderate rash while receiving therapy with efavirenz, and two of these patients discontinued because of rash.

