#### **9.2.5 Renal Insufficiency**

Tenofovir DF substitution should occur for a confirmed creatinine clearance  $< 50$  ml/min until an underlying etiology is determined. If no other etiology is determined or the renal insufficiency improves with holding tenofovir DF, tenofovir DF should be permanently discontinued.

Baseline serum creatinine will be the mean of the screening and entry values. If at any time serum creatinine is increased  $>1.5$ -fold above baseline, the serum creatinine should be repeated as soon as possible (preferably within one week). Participants with confirmed serum creatinine increases  $>1.5$ -fold above baseline should undergo an evaluation for potential causes of decreased renal function. Participants with confirmed increase in serum creatinine  $>1.5$ -fold above baseline should have serum creatinine monitored more frequently, at the discretion of the site investigator, until serum creatinine either stabilizes or decreases to  $\leq 1.5$ -fold above baseline. Drug dosing adjustments should be done based on the calculated creatinine clearance.

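### After week 24 the safety laboratory tests are scheduled only at week 48, so Arm 2 has one scheduled on-ART safety set, at study exit, contrary to Sections 7.4.3.6 and 8.5

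*Combined protocol and SAP*

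**What the plan says.** Section 7.4.2.2 makes the table binding: "On-study evaluations will occur according to the schedule of events as specified in Section 7.4.1". In the table used after Amendment Letter #1, both arms share the procedure rows, and week 0 is study entry. The arms are separated only in the blood-volume lines, one of them headed "Blood volumes (ml) for participants with deferred treatment".

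The arms start treatment at different points on that calendar. Section 7.4.2.1 says "Subjects randomized to Arm 1 must begin treatment within 72 hours after randomization, and preferably within 24 hours", so for Arm 1 study week and ART week nearly coincide. Section 6.3.1.3 says "Arm 2 will receive no treatment for 24 weeks and then receive 24 weeks of study treatment", and Section 6.3.1.1 places that treatment in weeks 25 to 48.

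Three parts of the text bear on testing during treatment:
- Section 8.5: "Routine monitoring of estimated creatinine clearance, urine glucose, and urine protein should be performed during" treatment with the elvitegravir-containing tablet. This applies to every patient, and no interval is given.
- Section 7.4.3.6: lipid values "should be recorded on the CRFs at baseline and every 12 weeks, regardless of toxicity grade".
- Section 9.2: action rules that depend on measured liver enzymes, lipase, triglycerides, creatinine and phosphorus.

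**The concern.** A calendar counted from enrolment follows drug exposure in Arm 1 but not in Arm 2. Arm 2 has its week 4, 8 and 12 tests while untreated. Its week-24 set is in effect a pre-treatment sample, and it then takes ART for 24 weeks with no further scheduled safety set until it leaves.

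Participant safety is at stake. Early renal, hepatic, pancreatic or phosphate changes can be silent, and the rules in Section 9.2 act on a laboratory value. Without a scheduled test, a silent abnormality gives those rules nothing to act on. There is also a consequence for interpretation: Section 12.7 asks whether the groups differ in safety and toxicity data, and on-treatment laboratory findings are looked for much less often in Arm 2.

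**Working it through.** **Duration.** Weeks 25 to 48 inclusive are 48 − 25 + 1 = 24 weeks, which reproduces the 24 weeks of Arm 2 treatment in Section 6.3.1.3.

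**Marked weeks (post-amendment table).** CBC: 0, 4, 8, 12, 24 and a last mark. Chemistry/LFT: 4, 8, 12, 24 and a last mark. Lipids: 0, 12, 24 and a last mark. Urinalysis: 0, 4, 12, 24 and a last mark. None of these rows has a mark from week 25 to week 40.

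**Placing the last mark.** In the text as extracted, it sits under week 44. The blood volume is 0 ml at week 44 and 121.5 ml at week 48 in both arms, so the mark belongs at week 48. Read literally at week 44, the interval would still be 44 − 24 = 20 weeks, with a single set.

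**Check against blood volumes.** In the pre-amendment table, week 12 (safety bloods, CD4 and viral load) is 21.5 ml and week 36 (CD4 and viral load) is 13 ml, a difference of 8.5 ml. In both tables, volumes ending in .5 occur only at weeks 4, 8, 12, 24 and 48, which are exactly the chemistry/LFT weeks. After the amendment, the draws at weeks 25, 26, 28, 32 and 40 are 50 or 100 ml, with no sign of a safety component, and week 36 stays at 13 ml. The pre-amendment table shows the same gap: 0 ml at weeks 28, 32, 40 and 44. It has a CBC mark extracted under week 28, but 0 ml is drawn then, so that mark is a column shift. Volumes cannot confirm the urinalysis row, which rests on its marks alone.

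**Tests after ART start.** Arm 1 ART week = study week. Arm 2 ART week = study week − 24, so week 48 is ART week 24.

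| Test | Arm 1, ART weeks | Arm 2, ART weeks | First 24 weeks on ART, Arm 1 vs Arm 2 | All follow-up, Arm 1 vs Arm 2 |
|---|---|---|---|---|
| CBC | 4, 8, 12, 24, 48 | 24 | 4 vs 1 | 5 vs 1 |
| Chemistry/LFT | 4, 8, 12, 24, 48 | 24 | 4 vs 1 | 5 vs 1 |
| Urinalysis | 4, 12, 24, 48 | 24 | 3 vs 1 | 4 vs 1 |
| Lipid panel | 12, 24, 48 | 24 | 2 vs 1 | 3 vs 1 |

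The comparison over the first 24 weeks is the fairer one, because Arm 1 is treated for twice as long. The first scheduled on-ART chemistry comes 24 − 4 = 20 weeks later after ART start in Arm 2 than in Arm 1.

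**Table against text.** Lipids every 12 weeks means weeks 0, 12, 24, 36 and 48, but the table omits week 36 for both arms. Section 8.5 asks for routine renal and urine monitoring during treatment. In Arm 2 the table supplies one on-treatment measurement, at the last visit.

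**The case against.** Several objections have force.

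- **Other routes to a test exist.** Sections 7.4.3.5, 9.1.4 and 9.2.2.2 provide for examination as indicated, lactate on suspicion, and amylase, lipase and triglycerides for symptoms. Section 7.4.3.7 requires a WBC and differential with every CD4 count, and a CD4 count is marked at week 36. A reader might infer that toxicity in Arm 2 would go undetected until exit. That is too strong: the gap concerns asymptomatic abnormalities. The week-36 WBC does not supply haemoglobin, platelets or chemistry.
- **The arms are tested equally by randomised group.** Both follow the same calendar, and Section 12.1 applies the adverse event definition to both from random assignment. A reader might infer that the safety comparison is biased as planned. It is not: the imbalance arises only if laboratory toxicity is compared by time on ART, and no such analysis is specified. Section 12.7 poses a monitoring question. The untreated Arm 2 panels are also the concurrent control for Arm 1.
- **Section 8.5 gives no interval and covers only the elvitegravir-containing tablet.** This is correct, but one measurement at exit can hardly serve as routine monitoring during treatment. The lipid text does state an interval.
- **Blank cells are weak evidence.** The hepatitis B row has no marks although testing is required. So a reader should not infer from the blank week-0 chemistry cell that no baseline exists: Section 5.3.2 requires creatinine, phosphorus, transaminases and lipase within 28 days before entry. Nor can missed rash at weeks 25 and 26 be inferred. The clinical-assessment row has lost a mark, weight and vital signs are taken at all visits, and the rash figures in Section 8.6 are for efavirenz. The gap found here is different, because four rows and the blood volumes agree.

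**Conclusion.** The concern holds as an inconsistency between the schedule and the text that affects participant safety. Under Section 7.4.1, a participant in Arm 2 who starts at week 24/25 has one scheduled on-ART set of CBC, chemistry/LFT, lipids and urinalysis, at week 48. In the first 24 weeks on ART this is one chemistry/LFT panel against four in Arm 1. The laboratory rules of Section 9.2 cannot be reached by schedule for an asymptomatic abnormality in Arm 2 before week 48.

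This rests on three assumptions:
- The last mark in each row belongs to week 48, as the blood volumes indicate.
- ART starts at the week-24 visit counted from enrolment. Section 4.2 mentions both diagnosis and enrolment as the starting point.
- The participant does not start early under Section 4.2. For those who do, the week-24 set is already on treatment and the gap is shorter.

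After the amendment, the point concerns only participants with recent infection who are randomised to Arm 2, because those with acute infection are offered immediate ART. The documents do not support a finding that toxicity would necessarily be missed or that the comparison by randomised group is biased.

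**What to change.** Reconcile the Section 7.4.1 table with Sections 7.4.3.6, 8.5 and 9.2, so that Arm 2's treated period carries scheduled safety tests consistent with the text. The sponsor's clinicians should decide the timing. Visits already exist at weeks 28, 32, 36, 40 and 44. Keep Arm 2's untreated panels, because they are the concurrent comparison for Arm 1. Resolve the week-36 lipid conflict for both arms in the same revision.

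In the analysis text, state that any between-arm comparison of on-ART laboratory toxicity under Section 12.7 (item 4) will account for the unequal number of on-ART tests, and keep it separate from the comparison by randomised group.

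The cost is an amendment to one table and the conflicting text, plus a few more routine panels in Arm 2. By the table's own volumes, the blood for one set is about 21.5 − 13 = 8.5 ml. No new visits are needed. After the amendment, blood is already drawn at weeks 28, 32, 36 and 40. Participants still on the pre-amendment schedule have a draw only at week 36 in that period, so a test at another visit would need an extra venepuncture.
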